Abbreviation	Definition
6-MP	6-mercaptopurine
ADA	anti-drug antibody
ADL	activities of daily living
AE	adverse event
AEC	absolute eosinophil count
ALT	alanine aminotransferase
ANCOVA	analysis of covariance
AST	aspartate aminotransferase
AUC	area under the curve
AUC _{0-inf}	area under the curve from time 0 to infinity
AUC _{0-t}	area under the curve from time 0 to time t
AZA	azathioprine
BCG	bacille Calmette-Guerin
β-hCG	beta human chorionic gonadotropin
BLRM	Bayesian Logistic Regression Model
BMI	body mass index
BP	blood pressure
C _{max}	maximum concentration
C _{min}	minimum concentration (trough)
CBC	complete blood count
CBT	continued blinded treatment
CL/F	apparent clearance
CMH	Cochran–Mantel–Haenszel test
CNS	central nervous system
CRF	case report form
CRO	contract research organization
CRP	C-reactive protein
DILI	drug-induced liver injury
DLT	dose-limiting toxicity
DRC	data review committee
ECI	events of clinical interest
ECG	electrocardiogram
eCRF	electronic case report form
EDC	electronic data capture
eGFR	estimated glomerular filtration rate
EOS	end of study
ET	early termination
EWOC	Escalation With Overdose Control
FAS	full analysis set
Fc	fragment crystallizable
FC	fecal calprotectin
GDPR	General Data Protection Regulation
GLP	Good Laboratory Practice
HBV	hepatitis B virus

Abbreviation	Definition
HBVcAb	HBV core antibody
HBVsAg	HBV surface antigen
HCV	hepatitis C virus
HCP	health care professional
HIV	human immunodeficiency virus
hs-CRP	high sensitivity C-reactive protein
HR	heart rate
HV	Healthy volunteer
IB	Investigator's Brochure
IBD	inflammatory bowel disease
IBT	initial blinded treatment
IBDQ	Inflammatory Bowel Disease Questionnaire
ICF	informed consent form
ICH	International Council for Harmonisation
IEC	independent ethics committee
IgG1	immunoglobulin G1
IL-2	interleukin-2
IL-2M	interleukin-2 mutein
IL-2R	interleukin-2 receptor
IL-2R α	interleukin-2 receptor alpha (also known as CD25)
IL-2R β	interleukin-2 receptor beta (also known as CD122)
IL-2R γ	interleukin-2 receptor gamma (also known as CD132)
IND	investigational new drug
INR	International Normalized Ratio
IPT	immunophenotyping
IRB	institutional review board
ITT	intent-to-treat
IWRS	interactive web response system
JAK	Janus kinase
LAIV	live attenuated influenza vaccine
LDH	lactate dehydrogenase
LLOQ	lower limit of quantification
MedDRA	Medical Dictionary for Regulatory Activities
MMR	measles, mumps, and rubella
MMRM	mixed-model-repeated measure
MMRV	measles, mumps, and rubella plus varicella
MTD	maximum tolerated dose
NCI CTCAE	National Cancer Institute Common Terminology Criteria for Adverse Events
NK	natural killer
NOAEL	no observed adverse effect level
OL	open-label
PBMC	peripheral blood mononuclear cell
PCR	polymerase chain reaction
PD	pharmacodynamics
PGA	physician global assessment
PK	pharmacokinetics

Abbreviation	Definition
PP	per protocol analysis set
PRO	patient-reported outcome
PT	prothrombin time
PTT	partial thromboplastin time
CCI	
RB	rectal bleeding
RHI	Robarts histopathology index
RO	receptor occupancy
S1P1	sphingosine-1-phosphate receptor 1
SAE	serious adverse event
SAF	safety analysis set
SAP	statistical analysis plan
SC	subcutaneous
SF	stool frequency
SF-36	Short Form-36
SOE	schedule of events
Spp	species
TB	tuberculosis
TEAE	treatment-emergent adverse event
TESAE	treatment-emergent serious adverse event
$t_{1/2}$	half-life
T_{max}	time at which the maximum concentration occurs
TMF	Trial Master File
TNF- α	tumor necrosis factor α
Treg	regulatory T cell
Tconv	conventional T cell
UC	ulcerative colitis
ULN	upper limit of normal
V_d/F	apparent volume of distribution
WHO	World Health Organization
WOCBP	women of child-bearing potential

1 INTRODUCTION

1.1 Ulcerative Colitis

Ulcerative colitis (UC) is a chronic inflammatory disease of the rectal and colonic mucosa that is characterized by periods of remission and relapse. UC often first appears during young adulthood, and typically presents with blood in the stool and diarrhea. Additional symptoms vary depending on the severity of inflammation and extent of disease and can include incontinence, increased frequency of bowel movements, mucus discharge, and abdominal discomfort. Up to 15% of patients initially present with severe disease, which is often associated with systemic symptoms, including fever, weight loss, and malaise. Furthermore, UC is associated with an increased risk of colorectal cancer (Ungaro, 2017). With poorly controlled disease, the risk of developing colorectal cancer increases with time (Jess, 2012).

The pathogenesis of UC is multifactorial, involving genetic predisposition, epithelial barrier defects, dysregulated immune responses, and environmental factors (Chang, 2020). Although the precise cause of UC is unknown, genetically susceptible individuals appear to have a dysregulated mucosal immune response to commensal gut flora and studies show that the homeostatic balance between regulatory T cells (Tregs) and effector T cells is disturbed in the colonic mucosa of patients with UC (Ordás, 2012; Ungaro, 2017).

The incidence and prevalence of UC have been increasing worldwide. In a systematic review of population-based studies, the highest reported prevalence values were reported in Europe and North America. In Europe, the incidence and prevalence ranged from approximately 1-58 per 100,000 person years and 2.4–505 per 100,000 person years, respectively and in North America, the incidence and prevalence ranged from 8.8–23.1 per 100,000 person years and 139.8–286.3 per 100,000 person years, respectively. Since the end of the 20th century, the incidence of both Crohn's disease and UC have also been increasing in newly industrialized countries in Africa, Asia, and South America (Ng, 2018).

1.2 Current Treatment Options for Patients with Ulcerative Colitis

While several treatment options are available and in development for the treatment of UC, there are currently no curative therapies. Goals of treatment include improved quality of life, reduction in long-term corticosteroid use, and minimization of cancer risk. Treatment of UC is dependent on the severity and the location of disease. Mild to moderate UC treatment may be treated with oral aminosalicylates, topical mesalamine, or topical steroids. For moderately active disease, oral corticosteroids and immunomodulators such as azathioprine (AZA) and 6-mercaptopurine (6-MP) may be utilized (Danese and Fiocchi, 2011). For more severe disease, tumor necrosis factor-alpha (TNF- α) antagonists such as infliximab (Remicade®), adalimumab (Humira®), and golimumab (Simponi®), or an α 4 β 7 integrin antagonist such as vedolizumab (Entyvio®) are often employed. Tofacitinib (Xeljanz®), an oral Janus kinase (JAK) inhibitor is also approved for the treatment of adult patients with moderately to severely active disease (Harbord, 2017). Although these agents may be effective in inducing disease remission, many are associated with toxicities. The use of 6-MP and AZA can result in neutropenia, pancytopenia, pancreatitis, nephrotoxicity, hepatotoxicity, and in rare cases, hepatosplenic T-cell lymphoma (Bousvaros, 2010; Carter, 2004; Chaparro, 2009; Turner and

Griffiths, 2011). Treatment with corticosteroids is associated with multiple adverse effects including cataracts, acne, hypertension, and diabetes. Furthermore, although effective in induction of response, many patients who initially respond to corticosteroids either become steroid-dependent or require surgery (Bradley and Oliva-Hemker, 2012; Tung, 2006).

1.3 PT101

Interleukin-2 muteins (IL-2M) are recombinant forms of IL-2 with amino acid substitutions designed to alter binding of IL-2 to the different interleukin-2 receptor (IL-2R) subunits. IL-2Ms that bind less favorably to IL-2R β and with greater affinity to IL-2R α induce a signal via IL-2R β and IL-2R γ only when IL-2R α is expressed and therefore preferentially activate Tregs. PT101 is a recombinant IL-2M that is fused at its C-terminus to the N-terminus of an effector function ablated human immunoglobulin G1 (IgG1) fragment crystallizable (Fc) domain using a 20 amino acid glycine/serine rich linker. Compared with wild-type human IL-2, the modified IL-2M component of PT101 contains mutations, which collectively lead to PT101 selectively activating Tregs over other cell types. The Fc component of PT101 contains alanine mutations in the base of the IgG1 hinge region, which reduce antibody effector functions.

A series of nonclinical studies have demonstrated that PT101 selectively activates and expands human and cynomolgus monkey Tregs without activating or expanding other populations of immune cells or inducing plasma proinflammatory cytokines. ^{CCI}

Maximum expansion of Tregs occurred between Days 8 and 10 after PT101 administration at all dose levels except the highest ^{CCI}

^{CCI} Treg numbers returned to near baseline by Day 29. No significant expansion in conventional T cells (Tconv), natural killer (NK) cells, or B cells was observed at any dose of PT101, and no meaningful change in plasma cytokine concentrations was observed. All adverse events (AEs) were Grade 1 or 2 in severity and most frequently involved cutaneous events including injection site reactions. ^{CCI}

Pandion Therapeutics, which initially developed PT101 and conducted the PT101-101 study, was acquired by Merck & Co. on April 1, 2021. PT101 is designated within Merck as MK-6194.

An additional multiple ascending dose (MAD) trial of MK-6194 (PT101) is currently in progress (MK-6194-003). This is a Phase 1, randomized, double-blind, placebo-controlled, MAD study in healthy subjects. The first subject was dosed in the trial in November 2021. The study is currently ongoing and plans to enroll up to 56 subjects in up to 7 panels of 8 subjects each (randomized 6:2 [PT101/MK-6194:PBO]) in a MAD design, after a recent protocol amendment to add additional dose escalation panels.

CCI

Dose escalation between panels is determined based on review of the safety data for at least 7 days after the last dose in each panel jointly by the investigator and the Sponsor. CCI

CCI

CCI

There have been no discontinuations related to AEs, serious adverse events (SAEs) have not occurred and stopping rules have not been met. The most common AEs have been injection site reactions and mild eosinophilia.

The primary objectives of MK-6194-003 are to evaluate the safety, tolerability and Treg pharmacodynamics (PD) of PT101 (MK-6194) in healthy subjects following multiple SC doses. Secondary objectives are to evaluate the pharmacokinetics (PK) and receptor occupancy of PT101 (MK-6194). Exploratory endpoints include exploratory PD biomarkers and ADA.

A complete summary of the clinical and nonclinical data relevant to the investigational product and its study in human subjects is provided in the PT101 Investigator's Brochure (IB).

1.4 Rationale for Current Study

Despite a number of available therapeutic options for patients with UC, there remains an unmet medical need because existing agents are limited by low efficacy and/or toxicities. Moderately to severely active UC remains a serious, life-threatening disease for which new therapies are needed to prevent disease progression, restore quality of life, and reduce the risk of colorectal cancer.

Autoimmune and inflammatory diseases result from disrupted immune homeostasis and inappropriate immune system activity, often driven by effector T cells. Tregs attenuate inflammatory processes by a variety of mechanisms that suppress the activity of effector T cells (Klatzmann, 2015). Studies show that the homeostatic balance between Tregs and effector T cells is disturbed in the colonic mucosa of patients with UC (Ordás, 2012; Ungaro, 2017). Furthermore, expansion of Tregs using repeated administration of low doses of IL-2 has shown preliminary evidence of clinical efficacy in small proof-of-concept clinical trials in patients with a variety of autoimmune diseases (Castela, 2014; Hartemann, 2013; He, 2016; Koreth, 2011; Rosenzwajg, 2015; Rosenzwajg, 2018; Saadoun, 2011). Low dose IL-2 resulting in at least 2-fold expansion in Tregs was associated with clinical response in an open-label trial in patients with moderate to severe UC (Allegretti, 2021). PT101 is an IL-2M that selectively activates Tregs over other cell types and may therefore represent a unique opportunity to rebalance the immune system in patients with a variety of autoimmune and inflammatory diseases including UC.

2 OBJECTIVES AND ENDPOINTS

Trial objectives and endpoints are listed below. Definitions of the efficacy and response assessments are provided in [Section 7.2](#).

2.1 Objectives

2.1.1 Primary Objective

- To evaluate the safety and tolerability of PT101 in subjects with active UC following multiple SC doses

2.1.2 Secondary Objectives

- To assess the PK of PT101 in subjects with UC following multiple SC doses
- To assess the PD of PT101 in subjects with UC following multiple SC doses
- To assess the immunogenicity of PT101 in subjects with UC following multiple SC doses
- To assess the PK/PD relationship of PT101 in subjects with UC following multiple SC doses

2.1.3 Exploratory Objectives

- To assess improvement in disease activity in subjects with UC following multiple SC doses of PT101
- To evaluate changes in PT101- and UC-associated biomarkers following multiple SC doses of PT101

2.2 Endpoints

2.2.1 Primary Endpoint

- Safety and tolerability as assessed by incidence of treatment-emergent adverse events (TEAEs), treatment-emergent serious adverse events (TESAEs), and changes in laboratory values, electrocardiograms (ECGs), physical exam findings, and vital signs through Week 12

2.2.2 Secondary Endpoints

- PK parameters of PT101 through Week 12
- PD parameters of PT101 through Week 12
- Anti-drug antibodies (ADA) to PT101 through Week 12
- The relationship between the PT101 PK and PD response

2.2.3 Exploratory Endpoints

- Mean change from baseline in modified Mayo Score at Week 12
- Mean change from baseline in total Mayo Score at Week 12
- Mean change from baseline in partial Mayo Score at Weeks 2, 4, 6, 8, 10, and 12
- Mean change from baseline in Roberts Histopathology Index (RHI) score at Week 12
- Mean change from baseline in UC-100 score at Week 12
- Mean change from baseline in fecal calprotectin (FC) at Weeks 4 and 12
- Mean change from baseline in high sensitivity C-reactive protein (hs-CRP) levels at Weeks 2, 4, 8, and 12
- Mean change from baseline in patient-reported outcome (PRO) measures at Week 12
 - Inflammatory Bowel Disease Questionnaire (IBDQ)
 - Short Form-36 (SF-36)
- Proportion of subjects achieving clinical remission at Week 12
- Proportion of subjects achieving endoscopic improvement at Week 12
- Proportion of subjects achieving clinical response at Week 12
- Proportion of subjects achieving symptomatic remission at Weeks 2, 4, 6, 8, 10, and 12
- Proportion of subjects achieving symptomatic response at Weeks 2, 4, 6, 8, 10, and 12
- Proportion of subjects achieving endoscopic remission at Week 12
- Proportion of subjects achieving histologic remission at Week 12
- Proportion of subjects achieving histologic response at Week 12
- Proportion of subjects achieving mucosal healing at Week 12
- Change from baseline in partial Mayo Score beyond Week 12
- Incidence and characterization of TEAEs and laboratory abnormalities beyond Week 12
- Changes in PT101- and UC-associated biomarkers

3 INVESTIGATIONAL PLAN

3.1 Summary of Study Design

This is a Phase 1b, adaptive, randomized, double-blind, placebo-controlled, multiple dose study in subjects with active UC. The study will be conducted at approximately 20 sites worldwide. A study schematic is presented in [Figure 1](#).

The study will enroll up to approximately 60 subjects with mildly to severely active UC in up to 6 cohorts of at least 10 subjects each (randomized 4:1 [PT101:placebo]) in a MAD design. There will be 3 planned cohorts (Cohorts 1–3) and up to 3 optional cohorts (Cohorts 4–6).

CCI
CCI Subject randomization will be stratified by prior advanced therapy use (yes or no). Enrollment of subjects with a prior history of inadequate response, loss of response, or intolerance to 2 advanced therapies as assessed by the Investigator will be capped at 20% of subjects per cohort.

A Data Review Committee (DRC) composed of unblinded members not involved in any way in the conduct of this trial will assess safety, PK, and PD data and provide recommendations on dose escalation/dosing regimen CCI study continuation, and enrollment of subjects into the 3 planned cohorts (Cohorts 1-3) and the 3 optional cohorts (Cohorts 4-6) as well as provide recommendations on dose and dosing regimen selection to inform future clinical development.

Because this is a Phase 1 assessment of PT101 in humans, the PK, PD, and safety profiles of the compound are still being elucidated. This protocol is therefore written with flexibility to accommodate the inherent dynamic nature of Phase 1 clinical studies. Refer to [Section 6.5](#) for examples of modifications permitted within the protocol parameters.

CCI
CCI New information, that was not available when the original protocol resented in the protocol, CCI

CCI This new information included 1) additional safety, PK, and PD data with PT101 in the FIH trial ([Sections 1.3](#) and [3.2.2](#)), 2) recently presented data of other IL-2M CCI sustained Treg expansion with good tolerability ([Section 3.2.2](#)), and 3) a new MAD trial of PT101 in healthy subjects (MK-6194-003) ([Section 1.3](#)) initiated in November 2021 to assess the safety, PK, and PD of PT101 administered as multiple doses CCI

CCI Safety data from MK-6194-003 was reviewed by the DRC to support initiation of Cohort 2 of this trial. PT-101 safety profile was considered acceptable by the DRC at CCI
CCI

With the modification of the CCI
CCI

In addition to the safety and PK rationale noted above,

[Redacted]

3.1.1 Initial Blinded Treatment Phase

3.1.1.1 Planned Cohorts (Cohorts 1–3)

Subjects in Cohorts 1-3 will be randomly assigned in a 4:1 ratio to receive PT101 or placebo at

[Redacted]
Enrollment in Cohorts 1–3 will occur sequentially. Progression from Cohort 1 to Cohort 2 per protocol will be based on DRC recommendations from all available unblinded safety, PK, and PD data reviewed from Cohort 1. All available unblinded safety data (all 8 subjects [PT101:PBO; 6:2] up to 1 week after the third dose of study drug received [Redacted] in a concurrent PT101 study conducted in a young adult healthy volunteer population (study MK-6194-003) was reviewed by DRC and considered acceptable. Recommendations from DRC may also include modification to the study design, including but not limited to assessment of a lower dose or repeating a dose/dosing regimen, changes to subject safety monitoring assessments, addition of sampling timepoints or closing enrollment in an ongoing cohort prior to completion, if appropriate.

[Redacted]
[Redacted] The DRC will review all safety and available PK and PD data from Cohort 2 and make recommendations for the next cohort (Cohort 3) regarding study continuation, dose escalation per protocol, or any modification to the study design. Moving sequentially from Cohort 1 through 3 requires

demonstration of adequate safety, guided by the in-cohort stopping rules and the cohort progression criteria (see Sections 3.1.1.4 and 9.3.4).

3.1.1.2 Optional Cohorts (Cohorts 4–6)

Up to 3 optional cohorts may be added following DRC review of all available data from the previous planned cohorts (Cohorts 1-3) to (a) assess additional dose levels of PT101 either in CCI and/or (b) repeat a previously studied dose level/dosing frequency that provides optimal expansion of peripheral Tregs while maintaining appropriate safety and tolerability. Operating principles for inclusion of optional cohorts in this study are listed below, and will be detailed in the DRC charter:

1. Optional cohorts will enroll subjects only after DRC recommendation and may be enrolled concurrently with the planned cohorts, if appropriate.

CCI

3.1.1.3 Dose-Limiting Toxicity

A dose-limiting toxicity (DLT) is defined as any treatment-related adverse event (AE) reported within 4 weeks from dosing that meets both of the following criteria:

- Grade 3 or higher in severity according to the National Cancer Institute (NCI) Common Terminology Criteria for Adverse Events (CTCAE), Version 5.0
- A shift of ≥ 2 NCI CTCAE grades from baseline (initial presentation of the AE)

3.1.1.4 Cohort Progression Criteria

Cohort progression criteria will be included in the overall data package reviewed by DRC to determine whether or not investigation of CCI

3.1.1.5 In-Cohort Stopping Rules

During a given cohort, if 3 or more subjects experience a DLT, 2 or more subjects experience similar DLTs, or 1 subject experiences a DLT of Grade 4 or higher in severity, further enrollment to the respective cohort will be paused pending DRC evaluation of all available safety, PK, PD, biomarker, and UC disease activity data. After the DRC convenes to review these data, they may recommend study continuation (with or without modification) or

termination of dosing within the cohort; DRC may also recommend de-escalation to lower doses/reduced frequency dosing regimen. If dosing within a cohort is terminated, the next-lower dose may be declared the maximum tolerated dose (MTD). Alternatively, an additional cohort at an intermediate dose may be added to better define the MTD.

The study may be stopped at the discretion of the Sponsor based on recommendations of the DRC. In all cases, necessary measures will be taken to ensure appropriate safety follow-up for all subjects in the trial.

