3.1.5 Dose Modification and Dose Schedule Deviation

If a subject has a DLT during study conduct, study drug dosing will be discontinued for that subject and the subject will be asked to return to the clinic 28 days after last dose of study drug for their ET visit. The AE triggering the DLT should be monitored through safety follow-up phone call and/or additional site visits as needed until the ET visit.

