3.1.6 Study Drug Interruption Considerations

When feasible, the medical monitor should be consulted prior to study drug interruption. The medical monitor must be informed of all cases of study drug interruption for medical reasons.

Study drug interruption must occur in the following circumstances:

- Intercurrent illness that would, in the judgment of the investigator, affect assessments of clinical status to a significant degree.
- A nonserious infection (e.g., acute upper respiratory tract infection, simple urinary tract infection)
- Positive urine pregnancy test (pending confirmation of pregnancy)

- Subject is scheduled for elective or emergency surgery (excluding minor skin procedures under local or no anesthesia)

Study drug administration may be resumed only after resolution of the condition causing interruption, and requires consultation with and approval by the medical monitor.

During the time of study drug interruption for any of the above, the subject may continue to have study visits and to take part in procedures and assessments if deemed medically appropriate by the investigator. Subjects with SARS-CoV 2 infection (or suspected infection) must follow local site specific regulations and the PT101-201 COVID-19 Risk Management Plan regarding study visits and procedures.

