 - New onset of clinically significant cardiovascular disease such as myocardial infarction, unstable ischemic heart disease, stroke, heart failure, or clinically significant changes in ECG
 - Subjects with a marked prolongation of the QTc interval identified on ECG during the study (e.g., increase in QTc to > 500 ms, or > 60 ms over baseline, [Appendix 8](#))
 - New onset of pulmonary edema, interstitial lung disease, or clinically significant dyspnea
 - New onset of clinically significant peripheral edema or reduced blood pressure (semi recumbent [supine or seated also acceptable, per site standard procedures]) SBP < 90 mmHg associated with symptoms such as lightheadedness, sustained over at least the next 90 minutes):

- SBP (supine or seated also acceptable) will be obtained as triplicate measurements every 30 minutes over the following 90 minutes (i.e. at 30, 60- and 90 minutes). If a subject's SBP remains < 90 mmHg for the median of all 3 measurements over the 90 minute period, this is defined as a sustained finding, and dosing will end for that particular subject.
- Reduction of estimated glomerular filtration rate (eGFR) < 60 mL/min confirmed on repeat measurement after at least 24 hours
- Serious infection requiring hospitalization or intravenous antibiotics
- Investigator or Sponsor determines that the subject will not benefit from further study drug
- Adverse event or laboratory or physical examination finding that in the opinion of the Investigator or Sponsor presents excessive risk to the subject
- Adverse event of Grade 3 or higher in severity that is attributable to study drug, or any unexplained \geq Grade 3 AE that is not reasonably related to the underlying disease process
- Subject becomes pregnant or plans a pregnancy within the study conduct
- Subject is unable to comply with the protocol requirements
- Sponsor or Regulatory Agency terminates the study

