Hospitalization:	The AE resulted in hospitalization or prolonged an existing inpatient hospitalization. Hospitalizations for elective medical or surgical procedures or treatments planned before the signing of informed consent in the study or routine check-ups are not SAEs by this criterion.
Disabling/ incapacitating:	An AE that resulted in a persistent or significant incapacity or substantial disruption of the patient's ability to conduct normal life functions.
Congenital anomaly or birth defect:	An adverse outcome in a child or fetus of a patient exposed to the molecule or study treatment regimen before conception or during pregnancy.
Medically significant:	The AE did not meet any of the above criteria, but could have jeopardized the patient and might have required medical or surgical intervention to prevent one of the outcomes listed above or involves suspected transmission via a medicinal product of an infectious agent.

Adverse Event Severity

AE severity should be graded using the NCI CTCAE, Version 5.0 (27 November 2017). The general categories for each grade are:

Grade	Severity	Alternate Description
1	Mild (apply event-specific NCI CTCAE grading criteria)	Asymptomatic or mild symptoms; clinical or diagnostic observations only; intervention not indicated
2	Moderate (apply event-specific NCI CTCAE grading criteria)	Minimal; local or noninvasive intervention indicated; limiting age appropriate instrumental ADL
3	Severe (apply event-specific NCI CTCAE grading criteria)	Severe or medically significant but not immediately life-threatening; hospitalization or prolongation of hospitalization indicated; disabling; limiting self-care ADL
4	Very severe, life-threatening, or disabling (apply event-specific NCI CTCAE grading criteria)	Life-threatening consequences; urgent intervention indicated
5	Death related to AE	Death related to AE

Abbreviations: AE=adverse event; ADL=activities of daily living; NCI CTCAE=National Cancer Institute Common Terminology Criteria for Adverse Events.

Note: Instrumental ADL refers to preparing meals, shopping for groceries or clothes, using the telephone, managing money, etc. Self-care ADL refers to bathing, dressing and undressing, feeding self, using the toilet, taking medications, and not bedridden.

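### After a treatment-related DLT of Grade 4 or higher, only enrolment and the affected subject's own dosing stop automatically; nothing holds the other subjects' doses until the DRC has reviewed the event

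*Protocol*

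**What the plan says.** Protocol section 3.1.1.5 and the synopsis give the same in-cohort stopping rule, with no visible redaction. There are three triggers: three DLTs, two similar DLTs, or one DLT of Grade 4 or higher. Section 3.1.1.3 makes treatment-relatedness part of the DLT definition. The severity table in section 7.6.1.1 defines Grade 5 as "Death related to AE".

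The automatic consequence for the cohort is that "further enrollment to the respective cohort will be paused pending DRC evaluation of all available safety" and other data. Ending dosing in the cohort comes later. It is one of the things the DRC may recommend "After the DRC convenes to review these data".

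For the affected subject, section 3.1.5 is definite: "study drug dosing will be discontinued for that subject".

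Section 3.1.6 opens its mandatory list with "Study drug interruption must occur in the following circumstances". The list covers intercurrent illness, a positive pregnancy test, planned or emergency surgery and "A nonserious infection (e.g., acute upper respiratory tract infection, simple urinary tract infection"). All of these are the subject's own conditions.

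Section 3.1.7 lists individual stopping rules. One allows a stop for a finding that "in the opinion of the Investigator or Sponsor presents excessive risk to the subject".

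SAP section 13 refers to the DRC charter for the detail of DRC review. It adds neither a dosing hold nor a time limit.

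**The concern.** The rule separates enrolment from dosing and acts automatically only on enrolment. That protects people who have not yet joined. It does not protect those already at the dose that has just produced a life-threatening or fatal drug-related event. Followed as written, the protocol lets them take their next scheduled dose before the DRC has judged whether the dose is acceptable, and a subcutaneous dose cannot be taken back.

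Once a cohort is fully enrolled there is no enrolment left to pause, so the automatic step then has no effect on anyone still being treated. Dosing at the cohort's dose can also continue for up to 9 months in the continued blinded treatment (CBT) and open-label (OL) phases (section 3.1.2).

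The contrast with section 3.1.6 is awkward. A subject's own simple urinary infection forces an interruption. A drug-related death in another subject at the same dose does not.

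**Working it through.** **Step 1. The provisions side by side.** The plan gives no figure on this point, so the main check is of the text.

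| Provision | Whose dosing it affects | Tied to a Grade 4+ DLT in another subject? |
|---|---|---|
| 3.1.1.5, pause | Nobody's (enrolment only) | Yes |
| 3.1.1.5, DRC recommendation | The cohort | Only after the DRC has met; optional |
| 3.1.5 | Affected subject | No |
| 3.1.6, mandatory interruption | Subject with the condition | No |
| 3.1.7, individual rules | Subject's own events, or investigator/sponsor judgement | No |
| 3.1.7 and 10.3.2, study termination | Everyone | No; discretionary |
| SAP 13 and 13.1 | Nobody's | No |

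No row gives an automatic interim hold for the other subjects in the initial blinded treatment (IBT), CBT or OL phase. Neither document sets a time for the DRC to convene.

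**Step 2. Illustration of exposure before a decision.** From the documents: a cohort of 10 randomized 4:1 has 8 subjects on PT101, so 7 others if one has the DLT. Assumed, because the interval is redacted and the review time is not given: interval 2 or 4 weeks, review 1 or 2 weeks, dosing days spread evenly, and nobody intervening by judgement. The case of 3 others still on treatment is also an assumption.

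- Expected further doses = n × review/interval.
- Chance that at least one other subject is dosed = 1 − (1 − review/interval)^n.

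| Review/interval | n = 7: doses; chance | n = 3: doses; chance |
|---|---|---|
| 1/4 | 1.75; 87% | 0.75; 58% |
| 1/2 or 2/4 | 3.5; 99% | 1.5; 88% |
| 2/2 | 7; 100% | 3; 100% |

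Seven is not a maximum. Cohorts are of at least 10, section 4.6 allows replacements, and former placebo subjects may be on PT101 in OL.

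**Step 3. Who would exercise judgement.** Section 3.1 says "The study will be conducted at approximately 20 sites worldwide". With equal enrolment (assumed), 9 × 1/20 = 0.45 of the other 9 subjects share the affected subject's site on average. Most are therefore under blinded investigators elsewhere.

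**Step 4. How often a hold would occur.** The documents give no risk of a Grade 4+ DLT, so p is an assumed risk per subject per 12 weeks.

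| p | One cohort, IBT, 8 on PT101: 1 − (1 − p)^8 | Three planned cohorts: 1 − (1 − p)^24 | One cohort, IBT, placebo events counted at the same p: 1 − (1 − p)^10 |
|---|---|---|---|
| 0.5% | 3.9% | 11% | 4.9% |
| 1% | 7.7% | 21% | 9.6% |
| 2% | 14.9% | 38% | 18.3% |
| 5% | 33.7% | 71% | 40.1% |

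The last column is there because relatedness is judged by a blinded investigator, so a placebo subject's event can count as a DLT.

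For all phases, assume full uptake, a constant hazard, 51 weeks on PT101 for 8 subjects and 39 weeks in OL for 2 former placebo subjects. That gives 8 × 51/12 + 2 × 39/12 = 34 + 6.5 = 40.5 twelve-week periods, and 1 − (1 − p)^40.5 = 18%, 33%, 56% and 87% per cohort. This is not an upper bound, because it leaves out placebo-triggered holds and replacements.

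**The case against.** The strongest reply is that subjects are not unprotected.

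- The excessive-risk clause in section 3.1.7 belongs to the sponsor as well as to the investigator.
- The sponsor is central and receives SAE reports within 24 hours (section 7.6.1.4).
- Selected firewalled sponsor personnel are unblinded, in part to monitor conduct (section 3.2.3).
- The sponsor may terminate the study at any time, and investigators may make changes to remove an immediate hazard (section 10.3.2).
- The safety record so far is mild. Single-dose adverse events were Grade 1 or 2, and the healthy-volunteer multiple-dose study reports no SAEs, no discontinuations due to adverse events and no stopping rule met (section 1.3).

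All of this stands, and it limits the point to the absence of an automatic hold. It does not remove it: each route depends on someone choosing to act, and none is linked to the trigger. The mild record lowers the expected frequency but does not exclude a Grade 4 event in patients with ulcerative colitis.

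The second reply also stands. A convening deadline directs the committee, so the DRC charter is a natural place for it, and the charter was not available. A reader might infer that the trial has no such deadline. The documents show only that the protocol and SAP state none. A deadline in the charter would shorten the gap, but it would not by itself hold a dose due the next day.

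**Conclusion.** The point holds. After a treatment-related DLT of Grade 4 or higher, the protocol automatically pauses enrolment and stops the affected subject. It does not hold the other subjects' doses until the DRC has reviewed the event. This rests on unredacted text and on no assumed number.

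Two stronger readings are tempting and are not supported. A reader might infer that the protocol directs the others to keep dosing. It is silent on this, so they may be dosed, and the sponsor or an investigator may stop them. A reader might also take the 87% to 100% for seven others as a risk of harm. It is only the chance that a scheduled dose falls inside an assumed review window if nobody steps in.

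The size is therefore illustrative: about 0.75 to 7 further PT101 doses over the assumed values. I would ask for the change as a cheap safety improvement. The triggers themselves are not at fault.

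**What to change.** Add to section 3.1.1.5 and to the synopsis:

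> If a DLT of Grade 4 or higher occurs, study drug dosing (PT101 and placebo) of all subjects in that cohort, and in any other cohort receiving the same or a higher dose/regimen, in whichever phase they are, is held until the DRC has given its recommendation. The DRC will convene within 7 days (or the time set in the charter). Dosing resumes on the DRC recommendation; the resolution requirement in section 3.1.6 does not apply to this hold.

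Three details matter:

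- The hold names placebo, because a hold on PT101 subjects alone would risk unblinding the cohort.
- It stays out of the section 3.1.6 list, where restart requires the causing condition to resolve. Another subject's death never does.
- It carries its own convening time, so that it is not open-ended.

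The counts and the other two triggers stay as they are.

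The cost is a few sentences, faster DRC meetings and some delayed doses. On the assumptions of step 2, each hold delays about 1.75 to 7 PT101 doses in a cohort with seven others on treatment, and more if another cohort is caught. This adds noise to the PK, PD and Week 12 data. Some holds will be set off by a placebo subject's event judged related under blinding, which the unblinded DRC can resolve. At an assumed 1% risk, about 8% to 10% of cohorts would have a hold during IBT.
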